5.3 Description of Intervention

This study will have both an experimental group and a control group.

5.3.1 Interventional Products

The control group will receive a placebo mist spray of sterile water. The product chosen for this is known as Nature's Tears Eye mist and is manufactured by Bio-Logic Aqua Research Technologies International Inc. This product was used as a placebo in a similar study. (Mace, S.E., 2016). This product is marketed to be used for the eyes and face but for the purpose of this study we will use it off label for its preservative and chemical free, non-allergenic, sterile properties. "With Nature's Tears EyeMist, the assembly process begins with a plastic, aluminized barrier bag which is attached to a plastic applicator nozzle. The rigid aluminum canister, with bag and nozzle in place, is then pressurized with nitrogen, an inert chemical that comprises 80% of the air we breathe. Nitrogen has a greater capacity to pressurize than oxygen or air, retards freezing, and microbes cannot live in nitrogen. The unit is then sealed with a rubber gasket. In the extremely unlikely event that the gasket fails, the unit would depressurize and simply not work. As long as the seal is intact, the contents remain clean and sterile." (Bio Logic Aqua Research Technologies International Inc, 2010.) The product has a four-year shelf life. (Bio Logic Aqua Research Technologies International Inc. 2010.) The experimental group will receive a spray that is manufactured by the Gebauer Company and is known as Ethyl Chloride Mist Spray Can P/N 0386-0001-02. This spray was selected because of its current use and patient preference in accessing port-a-catheter sites. The mist spray is indicated for temporary control of pain associated with injections, starting IV's and venipuncture, minor surgery and minor sports injuries. (Gebauer's Ethyl Chloride Spray, 2016).

The Nature's Tears Eye mist and Ethyl Chloride sprays used will be unidentifiable by the patients in the study. The Radiology department at Aultman hospital has agreed to cover the cost for the sprays needed in this study. The Gebauer Company indicates that each spray can may be used up to 50 times therefore for the purpose of this study it is estimated that 2 cans will be needed. The Bio-Logic Aqua Research Technologies

corporate office has agreed to send 2 cans of their Nature's Tears Eye mist at no charge.

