2.2 Secondary Objective

The broader implication to this study is to bring awareness to both caregivers and patients alike that there are options for pain management when IV insertions are needed and/or required. Furthermore, vapocoolant sprays are already being utilized for pain management in accessing port-a-cath sites in our Radiology department therefore this study could use the same spray as is indicated for its use in accessing IV insertion sites.

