5.0 STUDY DESIGN AND PROCEDURES

5.1 Design/Study Type

This is a single blind interventional study with a post design using a convenience sample of patients undergoing a Nuclear Medicine Stress Test at Aultman Heart Center.

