5.3.3 Intervention Administration

The researcher will access a peripheral IV site using the hospital protocol on inserting IV catheters. The researcher will select an IV site; the patient's skin will be cleansed prior to the intervention spray being applied per hospital protocol. The researcher will then spray the intervention spray made by the Gebauer Company according to the manufacturer's recommendations which is to spray the Ethyl Chloride aerosol can for 4 to 10 seconds from a distance of 3 to 9 inches (8-23 cm). Do not spray longer than 10 seconds. Spray the area for the time recommended or until the skin just turns white; do not frost the skin. With skin, taut, quickly introduce the needle because the numbing effect of ethyl chloride only lasts for a few seconds to a minute. (Gebauer's Ethyl Chloride Spray, 2016). Reapplication of the spray to the area when it has been too long or is no longer "numb" is also indicated by the manufacturer but for the purpose of this study the patient will only have the application applied once. For the control group the patient's skin will be prepared per hospital protocol then the researcher will apply the Nature's Tears Eye Mist to the area for 4-10 seconds prior to IV access.

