The sub investigators for the study will monitor the patient for any potential reaction to the ethyl chloride spray. The most common reaction being temporary skin color changes at the spray site. Furthermore, the sub investigators will monitor for the very rare but severe allergic reactions that could occur including rash; hives; itching; difficulty breathing; tightness in the chest; swelling of the mouth, face, lips, or tongue; decreased urination; symptoms of liver problems (eg, dark urine; loss of appetite; pale stools; stomach pain; unusual nausea or tiredness; yellowing of the skin or eyes). (Gebauer's Ethyl Chloride Spray, 2016). (See Attachment 6- The Gebauer Company's Safety Data Sheet (SDS).

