9.0 OUTCOMES AND SIGNIFICANCE

The intention of this study is to measure whether the use of a vapocoolant spray as an intervention increases the patient's satisfaction of IV insertion and decrease the patient's pain and/or perception thereof. This interventional study aims to show that the use of a vapocoolant spray prior to IV cannulation insertion will not only yield positive feedback from patients undergoing Nuclear Medicine scans but that such an intervention could change the traditional methods used for starting IV's in hospitalized patients. Furthermore, this study can be used to compare the use of a vapocoolant spray versus current practice which is not using a vapocoolant spray on IV insertions. This comparison will lead to awareness in pain management for IV insertions as well as determine if such a spray is cost effective and necessary.

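### The plan states that patients cannot tell the sprays apart, but describes nothing that hides the can or the skin colour change

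*Combined protocol and SAP*

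**What the plan says.** Section 5.1 sets the level of masking: "This is a single blind interventional study with a post design". Section 5.3.1 then asserts that the "sprays used will be unidentifiable by the patients in the study", and gives no method by which this is achieved.

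Three features do support the blind. The placebo is a sterile water mist that Section 5.3.1 says served as placebo in a similar study. Sections 5.3.2 and 6.3.1 have it refrigerated to imitate cold. Section 5.3.3 has it sprayed for 4-10 seconds, the same range as the active product.

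The plan also describes signs of the active spray. Section 5.3.3 gives the instruction "Spray the area for the time recommended or until the skin just turns white; do not frost the skin" and notes that "the numbing effect of ethyl chloride only lasts for a few seconds to a minute". Section 6.3.1, on reactions to ethyl chloride, adds: "The most common reaction being temporary skin color changes at the spray site".

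Under Section 5.4 the post-insertion outcomes are a 0-10 pain rating, a 1-5 satisfaction rating and a question on future use of a spray. Under Sections 5.2, 5.4 and 6.2 the sub-investigators apply the spray, insert the catheter, ask the questions, write down the answers and record which spray was used.

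**The concern.** Both research questions in Section 2.1 are answered by what the patient says. Since the person asking knows the arm, the patient's own ignorance of it carries most of the protection against expectation bias. The plan states that ignorance as a property of the sprays, yet elsewhere describes a visible sign of the active spray and no step that hides it.

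A patient who sees the label, or sees the skin pale, may infer the active spray, expect less pain and rate accordingly. A patient who sees no change may infer water. Either inference moves the arms apart in the direction the trial hopes to show. The covariate in Section 8.0, the pre-procedure perception, is collected before the spray and so cannot remove such a difference.

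**Working it through.** The plan gives no figure to reproduce, so the main check sets each possible cue beside whatever the plan does about it.

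| Cue open to the patient | Source | Measure described |
|---|---|---|
| Cold on the skin | 5.3.2, 6.3.1 | Placebo refrigerated |
| Length of spraying | 5.3.3 | Same 4-10 second range |
| Form of the product | 5.3.1 | Placebo is also a mist |
| Whitening or colour change | 5.3.3, 6.3.1 | None |
| Appearance of the can (two manufacturers) | 5.3.1 | None |
| Numbness | 5.3.3 | None |

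Three cues are addressed and three are not. Of the latter, the skin change and the can can be hidden by procedure; numbness cannot, because it is part of the active effect.

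**Hypothetical size.** Every bias input here is assumed; none comes from the documents.

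- Share of active-arm patients who recognise the spray: 25%, 50% or 75%.
- Shift in the pain score among them: 1 point.
- SD of the pain score: 2.5 points.
- Control patients who recognise water are ignored.
- Test: two-sided at 0.05, normal approximation, no true effect.
- Per-arm sizes follow from Section 6.1, with equal arms: 30/2 = 15 and 80/2 = 40.

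Between-arm shift in SD units: b = share x 1 / 2.5, which gives 0.25/2.5 = 0.1, 0.50/2.5 = 0.2 and 0.75/2.5 = 0.3.

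False-positive rate: 1 - Φ(1.96 - b/√(2/n)) + Φ(-1.96 - b/√(2/n)), where √(2/15) = 0.365 and √(2/40) = 0.224.

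| b (SD) | n = 15 per arm | n = 40 per arm |
|---|---|---|
| 0 | 5.0% | 5.0% |
| 0.1 | 5.9% | 7.3% |
| 0.2 | 8.5% | 14.5% |
| 0.3 | 13.0% | 26.9% |

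The pattern matters more than the values. For a given shift, recruiting towards 80 makes a spurious positive result more likely, because a larger sample estimates the biased difference more precisely.

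**The case against.** The best defence is that the plan took real care. A mist placebo, chilled and sprayed for the same time range, deals with cold, which is arguably the most obvious cue. The reference list shows the similar study as a double-blind trial of a vapocoolant. This stands, so a reader who infers that nothing shields the blind goes too far. It does not answer the point about the can and the skin: use of the product elsewhere does not show that this trial conceals either.

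Nor is whitening certain. The instruction allows spraying for the recommended time or until the skin whitens, and Section 6.3.1 ranks colour change among reactions without giving a frequency. The documents therefore support a cue that may occur, not a blind known to be broken.

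A reader might also infer that patients know the spray already, since Section 2.2 says "vapocoolant sprays are already being utilized for pain management in accessing port-a-cath sites in our Radiology department". The documents do not support that. The use is for port access, Section 9.0 describes "current practice which is not using a vapocoolant spray on IV insertions", and nothing shows that the enrolled stress-test patients have met the product. Telling patients before consent that the comparison is vapocoolant against placebo is ordinary practice and identifies neither spray.

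Finally, Section 5.4 lists no question on which spray the patient believes was used, and Section 8.0 plans no check of the blind. The text of Attachment 4 is not available here, so such an item on the form cannot be ruled out. It would in any case be of limited use: a correct guess can reflect genuine pain relief, so it cannot separate expectation from effect.

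**Conclusion.** The point holds in a limited form. The claim that patients cannot identify the sprays is only partly backed by procedure: cold, spray time and product form are addressed, while the can and the possible skin change are not. Because both main outcomes are self-rated and the researcher who collects them is unblinded, this gap should be closed before recruitment. The trial can run without the change, but a positive result would be harder to defend.

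The size of any bias is unknown. The rates shown above rest wholly on assumed recognition, expectation effect and SD, and should not be read as an estimate for this trial. The conclusion does not depend on them; it rests on comparing Section 5.3.1 with Sections 5.3.3, 6.3.1 and 6.2.

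**What to change.** Replace the bare statement in Section 5.3.1 with a procedure that applies identically in both arms:

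- Cover the two cans alike.
- Have the patient look away, or screen both the can and the insertion site, from just before the spray until the post-insertion answers are recorded.
- Place any screen so that the patient can still see the pain and satisfaction scales of Section 5.2 and the researcher can still see the skin.

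Optionally, add one final item to Attachment 4, asked after all ratings: which spray does the patient think was used (numbing, water, do not know)? Report the answers by arm, descriptively only, and do not use them to exclude patients or adjust the analysis. Patients are seen only on the day of the test, so the item has to be asked then.

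The cost is one procedural sentence, can covers, a simple screen or instruction and, if wanted, one form item. Two limits remain and should be acknowledged: numbness cannot be masked, and the researcher who collects the ratings still knows the arm.

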5.3.2 Product Handling and Storage

The manufacturer of Nature's Tears Eye Mist MDS report (see Attachment 7) indicates that the can should be stored at room temperature and should not be stored at temperature's greater than 50°C (120°F). (Biologic Aqua Technologies, 2013). For the purpose of this study the Nature's Tear Mist spray will be refrigerated to "mimic" a cold spray. There are no documented contraindications that refrigeration would affect the sterility or application of the spray. The refrigerator is located in the Nuclear Medicine department's "Hot Lab" that is monitored by temperature control and is in a locked room. The Gebauer Company's Safety Data Sheet (SDS) (see Attachment 6) indicates that the ethyl chloride spray should be stored in cool, dry well ventilated area. Protect against physical damage. Do not subject to temperatures above 120°F (50°C). Do not store near high frequency ultrasound equipment or non-explosion proof electrical equipment. (Gebauer Company, 2013.) This product will be stored in a locked cabinet located in the Nuclear Medicine Department's scan room which is temperature controlled at 72°F.

5.3.3 Intervention Administration

The researcher will access a peripheral IV site using the hospital protocol on inserting IV catheters. The researcher will select an IV site; the patient's skin will be cleansed prior to the intervention spray being applied per hospital protocol. The researcher will then spray the intervention spray made by the Gebauer Company according to the manufacturer's recommendations which is to spray the Ethyl Chloride aerosol can for 4 to 10 seconds from a distance of 3 to 9 inches (8-23 cm). Do not spray longer than 10 seconds. Spray the area for the time recommended or until the skin just turns white; do not frost the skin. With skin, taut, quickly introduce the needle because the numbing effect of ethyl chloride only lasts for a few seconds to a minute. (Gebauer's Ethyl Chloride Spray, 2016). Reapplication of the spray to the area when it has been too long or is no longer "numb" is also indicated by the manufacturer but for the purpose of this study the patient will only have the application applied once. For the control group the patient's skin will be prepared per hospital protocol then the researcher will apply the Nature's Tears Eye Mist to the area for 4-10 seconds prior to IV access.

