5.4 Data Collection

The questionnaire (See Attachment 4- Patient Questionnaire and Researcher Documentation Form) will include the following questions prior to the use of the intervention:

- 1.) Using the visual analog scale provided how would you rate your pain the last time you remember having an IV inserted?
- 2.) Using a 0-5 Likert scale please rate how satisfied you were the last time you remember having an IV inserted?
- 3.) Do you think it is important to control the pain of starting an IV?

Once the IV has been placed the researcher will ask the patient the following questions:

- 1.) Using the same 0-10 pain scale how would you rate this IV insertion?
- 2.) Using the same 1-5 satisfaction scale how satisfied were you with this IV insertion?
- 3.) Would you choose to have a spray used again if you needed to have an IV inserted in the future?

The researcher will document the patient responses as well as the angiocatheter size, angiocatheter location, numbers of IV start attempts, the time that the intervention was applied and what interventional spray was used. (See Attachment 4- Patient Questionnaire and Researcher Documentation Form). This information will be coded and will be used to analyze study results post intervention. The presence of adverse events will be monitored and documented for 120 minutes following the IV insertion.

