6.0 STUDY ADMINISTRATION

6.1 Description of Study Process

This study will be conducted using patients who are ordered to undergo a Nuclear Medicine Stress Test. These patients will only be seen in this department the day that the stress test exam is performed. The anticipated time it will take to gather the patient's information, conduct the recruitment and consent portion of the study is approximately 30 minutes per patient. This study will use a convenience sample of patients over a 4-month period. The target goal is 30 patients; however, researchers may recruit up to 80 patients.

Once the determination has been made by the researcher that the patient is a candidate for the study the patient has consented they will be assigned to either the control group or experimental group through a computerized randomization sheet. Both the control group and experimental group will be equally represented. Once the IV has been placed regardless of what intervention was used the patient will then be asked by the researcher the questions as stated above.

The participants will only have the intervention used on a first attempt IV access. If the participant has to have additional attempts by the researcher to start an IV, their study will automatically be excluded.

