6.2 Data Quality and Confidentiality

The information obtained during this study will remain confidential and will be stored in a file cabinet with a key lock. [name] and [name] the Sub- investigators of this study under the supervision of the Principle Investigator [name] will be responsible for the following:

- 1). Explaining the study to potential participants along with conducting the consent process with the patient.
- 2). Asking related questions to consented participants regarding the research information obtained during the conduction of this study.
- 3). The medical review of patient health information determine eligibility.
- 4). Administration of the vapocoolant spray and placebo spray prior to IV access.
- 5). Performing IV access on study participants
- 6). Identifying any adverse reaction to the intervention being used. All adverse events will be reported to and managed by the Principle Investigator.

These responsibilities performed only by the Sub Investigators will ensure that there will be no threat to the validity of the study being performed and its study results. Data for this study will be kept only as long as the study is being conducted and analyzed for results. Once this information has been obtained all records will be discarded in accordance with hospital policy and applicable regulations. Within the consenting process the patient will be made aware that their information will be kept confidential and that the patient has the right to end their participation in the study at any point.

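### Nothing requires the IV site to be fixed before the unblinded operator knows the arm, and the protocol text sets no rule for catheter size

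*Combined protocol and SAP*

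**What the plan says.** Section 5.1 sets the blinding: "This is a single blind interventional study with a post design". Section 5.3.1 says whom it covers: the "sprays used will be unidentifiable by the patients in the study". No section says that the operator is blinded.

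Section 6.2 gives the sub-investigators both "Administration of the vapocoolant spray and placebo spray prior to IV access" and "Performing IV access on study participants". Section 5.4 has the researcher document "what interventional spray was used".

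On timing, Section 6.1 says that once a patient is found eligible and has consented, "they will be assigned to either the control group or experimental group through a computerized randomization sheet". Section 5.3.3 describes the insertion. It is done under a hospital protocol that is cited but not reproduced. "The researcher will select an IV site" comes first, then skin cleansing, then the spray.

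Catheter size appears only in Section 5.4, in the list of items to document: "the angiocatheter size, angiocatheter location, numbers of IV start attempts". That section adds that the recorded information will be used in the analysis, without saying how. Section 8.0 names one covariate, pre-procedure perception.

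**The concern.** The arms are meant to differ only in the spray. It is reasonable to suppose that the site of the vein and the size of the catheter also affect how much an insertion hurts and how satisfied the patient is, although the documents do not say so. If someone who knows the arm sets either of them, the comparison may become the spray plus whatever site or size tended to go with it.

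The direction cannot be predicted. An operator might look for an easier vein for a patient known to be getting water, or might accept a more sensitive site because the skin has been cooled. Neither needs any intent to bias the result.

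A separate person asking the outcome questions would not remove this route, because it acts on the insertion and not on the rating. Concealing the next assignment would not remove it either, if the site is still chosen after the assignment is known.

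**Working it through.** The plan has no figure of its own here, so the check is mainly a reading of the sections side by side.

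**1. Does the operator know the arm?** Yes. Blinding is described for patients only (5.1, 5.3.1). The person who sprays also cannulates (6.2) and writes down which spray was used (5.4). The cans are kept in different places: the water in a refrigerator in the Hot Lab, the ethyl chloride in a locked cabinet in the scan room (5.3.2).

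**2. Does site choice follow assignment?** On the natural reading, yes. Section 6.1 puts assignment after consent, and Section 5.3.3 makes site selection the first step of the insertion. The order comes from joining two sections. Neither says when the randomization sheet is consulted relative to site choice.

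**3. Who sets catheter size, and when?** The documents do not say. Size is an item to record (5.4) and nothing more.

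**4. Does the analysis deal with it?** No method is given for site or size, and the only named covariate is pre-procedure perception (8.0). Values chosen once the arm is known may themselves result from the arm, so conditioning on them does not cleanly restore the randomised comparison.

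**5. Is there a second route?** Possibly. Section 6.1 excludes any patient who needs a further attempt. If site choice depends on the arm and affects first-attempt success, it also affects who is analysed.

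**Illustration of size.** None of the inputs below is in the documents except the totals of 30 and 80 and the equal arms (6.1).

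Bias = (extra pain from the more painful insertion) × (difference between arms in the share of such insertions).

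| Assumed extra pain, points | Assumed difference in share | Bias, points |
|---|---|---|
| 0.5 to 1.5 | 20 to 40 percentage points | 0.5 × 0.2 = 0.1 to 1.5 × 0.4 = 0.6 |
| 1 to 2 | 10 to 30 percentage points | 1 × 0.1 = 0.1 to 2 × 0.3 = 0.6 |

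Standard error of the difference between arms = SD × √(2/n per arm). With an assumed SD of 2:

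- 15 per arm: 2 × √(2/15) = 0.73
- 40 per arm: 2 × √(2/40) = 0.45

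The largest bias, 0.6, is below one standard error at 30 patients and above it at 80.

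With no true effect and a two-sided 5% test, the false-positive rate by normal approximation is 1 − Φ(1.96 − bias/SE) + Φ(−1.96 − bias/SE):

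| Bias, assumed SD | 30 patients | 80 patients |
|---|---|---|
| 0.1, SD 3 | 0.051 | 0.053 |
| 0.6, SD 2 | 0.13 | 0.27 |

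As a share of a half-SD effect, the bias runs from 0.1/(0.5 × 3) = 7% to 0.6/(0.5 × 2) = 60%. No corresponding figure was worked out for satisfaction.

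**The case against.** The strongest reply has four parts.

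**The hospital IV protocol may already limit site or size in both arms.** This cannot be ruled out, because that document is not reproduced. But Section 5.3.3 still has the researcher select the site, so some discretion appears to remain. If the hospital protocol does fix these choices, one sentence saying so would answer the point.

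**The first-attempt rule in Section 6.1 restrains the operator.** Losing a patient after a failed first attempt is a reason to pick the most reliable vein in either arm. This is fair, and it makes a large imbalance less likely. It does not exclude one.

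**Size and location are recorded, so an imbalance would be visible.** True, and useful for interpretation. Seeing an imbalance does not remove the bias it causes.

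**The size of the bias is assumed throughout.** This stands in full. The top of the range needs both upper assumptions at once, and the bottom is negligible.

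A reader might also infer that the operator chooses the catheter size after assignment, or that size and location are written down only after insertion. The documents support neither. Section 5.4 gives no decision rule or timing for size, and the layout of Attachment 4 cannot be seen.

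**Conclusion.** The point holds as a gap in procedure. An operator who knows the arm selects the site, nothing requires that choice to be made before the arm is known, and the protocol text is silent on who chooses size and when. Differences in site, and possibly in size, could therefore arise from the allocation and could bias pain and satisfaction in either direction.

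The conclusion rests on two things that are not stated outright: the order of assignment and site choice, inferred from Sections 6.1 and 5.3.3, and the supposition that site and size affect pain. The figure of 0.1 to 0.6 points is illustrative only. A reader might infer that the comparison will be biased. The documents show only that it could be.

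The change is worth making because it costs little and because later adjustment is a poor substitute.

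**What to change.** In Sections 5.3.3 and 6.1, state that after consent and the pre-insertion questions the researcher records the intended IV site and catheter size on the documentation form, and only then consults the randomization sheet. Any later change of site or size is recorded with its reason. Intended and actual site and size are tabulated by arm for all assigned patients, including those excluded after a failed first attempt. The intended values are then true baseline variables and may be used as covariates. If the hospital IV protocol already fixes either item, say so and cite the rule.

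This works only if the researcher cannot see the next assignment beforehand. The plan describes no concealment of the sheet, so the amended text should cover that too.

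The change sets no clinical rule on site or size and needs no extra patients, visits or staff. It takes a few sentences in the protocol and entries for the intended values on the documentation form. The downside is a short delay while the assigned can is collected from its storage place after the site has been chosen.

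### Section 5.3.3 asks for taut skin and quick needle entry in the ethyl chloride arm only, from an operator who knows the arm: an avoidable performance-bias risk of unknown size

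*Combined protocol and SAP*

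**What the plan says.** Section 5.3.3 opens with a rule for all participants: "The researcher will access a peripheral IV site using the hospital protocol on inserting IV catheters". It then gives the manufacturer's directions for ethyl chloride: a spray time of 4 to 10 seconds, a distance of 3 to 9 inches, a stop when the skin whitens, and this needle instruction: "With skin, taut, quickly introduce the needle because the numbing effect of ethyl chloride only lasts for a few seconds to a minute". The control arm has skin preparation per hospital protocol, after which the researcher applies the "Eye Mist to the area for 4-10 seconds prior to IV access". Nothing is said for control about distance, skin tension or how soon the needle follows.

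Section 5.1 states: "This is a single blind interventional study with a post design". Section 5.3.1 describes the two sprays as indistinguishable to patients and says nothing of operators. Section 6.2 assigns spraying, IV insertion and questioning to the same sub-investigators.

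Under section 5.4 the patient is asked: "Using the same 0-10 pain scale how would you rate this IV insertion". A matching question covers satisfaction. The process items listed there are catheter size, catheter location, number of attempts and "the time that the intervention was applied and what interventional spray was used". No needle-entry time is listed.

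**The concern.** The trial is meant to show what the spray does to pain and satisfaction. As written, the arms differ in the spray and also in two instructions about the needle. Both outcomes are the patient's rating of the whole insertion, so firm traction or a brisk entry could affect the score whether or not the skin is numb.

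Handling happens after assignment, so randomisation does not balance it. The covariate named in section 8.0, pre-procedure perception, is collected beforehand and cannot adjust for it. If an operator who knows the arm reads the taut-skin and quick-entry wording as applying to ethyl chloride alone, part of any difference between arms could come from handling.

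A second, smaller matter concerns a null result. The protocol describes a short numbing period and allows only one application. With no entry time among the listed items, a reader could not tell an ineffective spray from a needle placed too late.

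**Working it through.** The plan states no figure on this point, so the check is a comparison of texts.

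**Step 1. Instructions by arm (section 5.3.3).**
- Hospital IV protocol: both arms.
- Spray time of 4 to 10 seconds: both arms.
- Stop at skin whitening: ethyl chloride only. This is correct, because it is a safety and effect end point of that product.
- Spray distance of 3 to 9 inches: ethyl chloride only.
- Skin held taut: ethyl chloride only.
- Quick needle entry: ethyl chloride only.

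The last two concern how the needle is inserted, so they carry the point. Distance does not: no route is given by which the distance of a water mist would change insertion pain. Matching it helps consistency and keeps the two procedures alike to the patient.

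**Step 2. Does the operator know the arm?** The protocol does not say so in words, but five statements point the same way:
- The design is single blind (5.1).
- Masking is described for patients only (5.3.1).
- The water can is refrigerated in one room, and the ethyl chloride is kept in a cabinet in another at 72°F (5.3.2).
- The whitening end point applies to one product (5.3.3).
- The researcher writes down which spray was used (5.4).

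Because the same sub-investigators spray and insert (6.2), the person holding the needle knows the assignment.

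**Step 3. Can handling reach the outcome?** Yes in principle. The questions in 5.4 are about the insertion, not the spray, and the rating is subjective.

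**Step 4. What could be checked afterwards?** The application time in 5.4 may mean a clock time or a spray duration. Neither gives the interval to needle entry. An insertion time may exist elsewhere, since "The presence of adverse events will be monitored and documented for 120 minutes following the IV insertion", but it is not among the listed items.

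**Step 5. What would the interval show?** It would show whether ethyl chloride needles went in within the numbing period the protocol quotes. It would not show traction or needle technique. In the control arm the documents describe no numbing that a delay could lose. Its use is therefore treatment fidelity.

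**Scale of the change.** Section 6.1 gives 30 to 80 patients in equal groups, so 30/2 = 15 to 80/2 = 40 per arm, and 30 to 80 timed entries in all. No bias size is computed, because the documents offer no basis for one.

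**The case against.** The strongest reply is that the difference may be one of wording only. The hospital IV protocol governs both arms and may already require traction and prompt entry. If it does, the ethyl chloride sentence repeats standard technique. That sentence is also taken from the manufacturer and gives its own reason: the numbing fades. Placebo has no numbing to lose, and quick entry most naturally means a short delay after spraying, not different needle work. Limiting the tasks to the sub-investigators (6.2) also limits variation between operators in both arms. Finally, Attachment 4 is not reproduced and might hold an entry time.

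Much of this stands. It rules out the stronger reading a reader might infer, that control needles will be inserted differently or that the result will be biased. The documents show neither. It also rules out treating the spray-to-needle interval as a test for performance bias: similar intervals would not exclude such bias and different ones would not establish it. Late needling is further limited because the site is chosen before spraying (5.3.3) and the spray is used only for a first attempt (6.1).

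What remains is that the section applies the hospital protocol to everyone and then states traction and prompt entry for one arm alone, to an operator who knows the arm. A product-specific reason for quick entry does not explain why traction should be written for one product only, and it gives no reason against writing both for both arms. Section 6.2 counts the task restriction as protection for validity, but that restriction does nothing about knowledge of the arm.

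**Conclusion.** The point holds as an avoidable risk of performance bias in patient-rated pain and satisfaction. Its size and direction are unknown, and no difference in technique is demonstrated. It rests on two assumptions: that the operator knows the arm, which is a strong inference from sections 5.1, 5.3.1, 5.3.2, 5.3.3, 5.4 and 6.2; and that the hospital IV protocol does not already make traction and prompt entry the same in both arms, which cannot be checked. If that protocol does cover them, the change is only a clarification.

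A reader might take the missing entry time as a failure to measure the bias. It is not: the interval bears on whether ethyl chloride was delivered as intended, and its absence from the list in 5.4 is a secondary gap. The case for acting is that common wording costs almost nothing, and insertion timing that was never recorded cannot be recovered later.

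**What to change.** In section 5.3.3, replace the two descriptions with one procedure for both arms: spray from 3 to 9 inches for 4 to 10 seconds, hold the skin taut, and enter promptly once spraying ends. Keep only the skin-whitening stop, with its caution against frosting, as specific to ethyl chloride. The common distance is mainly for consistency and patient masking.

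As a secondary step, add to section 5.4, and to Attachment 4 if it is not already there, the seconds from end of spray to first needle entry. Report it descriptively by arm as a fidelity check. Do not exclude or subset patients on it: the interval arises after assignment and is under the control of an operator who knows the arm, so selecting on it would undermine the randomised comparison.

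The cost is a short protocol and form amendment and one timed entry per patient, with slight extra attention to a timer during the procedure. No extra patients, staff or procedures are needed. The change does not blind the operator and does not record traction, so some risk of performance bias remains and should be acknowledged when results are reported.
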